Oct 18 2024

Clinicaltrials: Study 00011755

INVESTIGATOR-SPONSORED STUDY

The Use of Real-Time Continuous Glucose Monitoring (RT-CGM) in Gestational Diabetes

[name], [name], [name].

Division of Metabolism, Endocrinology and Nutrition

**Department of Medicine
University of Washington
[name]
[name]
[name]**

Correspondence to:

**[name]
Assistant Professor
Email: [contact]
[contact]**

Table of Contents

A. Specific Aims/ Hypothesis.....	4
B. Background.....	4
C. Significance:	4
D. Research Recruitment and Population.....	5
E. Statistical Considerations.....	6
F. Inclusion/Exclusion Criteria.....	7
G. Diagnosis of GDM.....	8
H. Study Design.....	9
I. Randomization.....	12
J. Study Procedures, Materials and Devices.....	13
K. Measurements.....	14
L. Collection of Human Biological Specimens.....	15
M. Questionnaires.....	16
N. Glucose/CGM Data /Evaluation Measures.....	17
O. Antenatal Ultrasound Markers.....	17

P. Risks and Side-Effects.....	17
Q. Benefits.....	18
R. Conflict of Interest.....	18
S. Confidentiality.....	18
T. Compensation.....	19
U. Appendixes.....	19

RESEARCH PROTOCOL

TITLE: A Study on the Use of Real-Time Continuous Glucose Monitoring (RT-CGM) in Gestational Diabetes

A. Specific Aims/ Hypothesis: We hypothesize that use RT-CGM in those with gestational diabetes will improve/ reduce glycemic variability in pregnancy and potentially improve fetal and maternal outcomes.

Aim 1. Evaluate if Real Time Continuous Glucose Monitoring improves mean glucose, time in range, time above and below range, mean amplitude of glycemic excursions (MAGES) and standard deviation of blood sugars and coefficient of variation (CV)

Aim 2. Evaluate if improved glycemic variability improves fetal and maternal outcomes in pregnancies affected by gestational diabetes.

Aim 3: Evaluate participants' perception of RT-CGM use in pregnancies affected by gestational diabetes.

Aim 4: Evaluate nutritional and lifestyle changes in GDM and pregnancy and effect of RT-CGM

Aim 5: Evaluate if RT-CGM decreases need for initiation of oral diabetes medication and/or insulin. If insulin initiated, evaluate if RT-CGM reduces cumulative insulin dose.

Aim 6: Evaluate nocturnal hypoglycemia in pregnancy and if RT- CGM lessens nocturnal hypoglycemia

B. Background and Significance

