Use of continuous glucose monitoring (CGM) has increased given improved sensor accuracy, greater convenience and ease of use, and expanding reimbursement. However, utilization of CGM technology in clinical practice, especially in gestational diabetes, remains low given paucity of clinical data. In February 2019, the Advanced Technologies & Treatments for Diabetes Congress convened an international expert panel to discuss this issue but because of the lack of evidence for CGM targets for women with gestational diabetes mellitus (GDM), percentages of time spent in range, below range, and above range were not included (1). Currently data are limited and studies are needed to show efficacy of this technology and thus we are conducting a pilot study of CGM in gestational diabetes in order evaluate maternal and fetal outcomes in the setting of CGM use in gestational diabetes.

C. Preliminary Studies

Many studies have demonstrated that RT-CGM can be used in adults and children with both Type 1 and Type 2 diabetes resulting in improvement in HbA1c and/or a reduced frequency of hypoglycemia (2-4). Our initial research showed that the use of RT-CGM serially over 3 months improved HbA1c by an average of 1.0% in subjects with Type 2 diabetes on no prandial insulin (5). Nutrition and activity changes were not measured but the 3-month HbA1c improvement was sustained for another 9 months without further RT-CGM intervention (6) but otherwise data is limited in type 2 diabetes and CGM use. Similarly, data in GDM and CGM use is limited: The largest study on GDM did show that standard deviation of blood glucose, mean amplitude of glycemic excursion (MAGEs) , and mean of daily differences values were significantly lower in the CGM group compared with those in the routine care group ($P < .001$) (7). A more recent study which reviewed

correlation between third trimester glycemic variability in non-insulin-dependent gestational diabetes mellitus failed to show any adverse pregnancy and fetal outcomes but did not report mean glucose (8). One recent study highlights that even more stringent targets may be needed (9) and another the importance of CGM mean glucose and time in range especially overnight (10) where data from traditional fingersticks is not typically available.

D. Research Recruitment and Population

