The HbA1C outcome was used for the sample size calculation. Since we are collecting HbA1C every 8 weeks, we are able to leverage the repeated measures design in the estimation of the sample size needed for this study. This allows us to gain efficiency and reduce the number of subjects needed. Thus, for an effect size 'f' of 0.14, which is between small (0.10) and medium (0.25), an alpha of 0.05 and power of 0.80, we need a total of 92 study subjects. Allowing for some attrition in study subjects, we are planning to enroll 100 patients.

Note that this type of sample estimation requires that we specify the variance across observations (sphericity) and the correlation across observations. We specified both at 0.60. We calculated sample size using G*Power.

Data Analysis Plan

The data analysis will start with completion of the **CONSORT** diagram, with an analysis of differences between those who completed the study and those who did not (t-tests and chi-square tests, as needed, comparing basic demographics and baseline health characteristics), so that the researchers in this area can understand the extent to which our study contains bias.

Next, we will calculate summary statistics (means, medians, proportions, etc.) of all baseline measurements, overall and by study arm, so that we can fully characterize the study cohort.

Using the CGM data, we will graph each participant's trajectories over time and review each, examining for major patterns in the trajectories. Note that typically statistical analyses emphasize homogeneity in the data; however, this approach will allow for understanding of heterogeneity. As part of this examination of the CGM data, the analysis will calculate each participant's measures of glycemic variability (such as mean amplitude of glycemic excursions, coefficient of variation, etc.), HbA1C values, and fructosamine values and overlay them on each graph. This part of the analysis is predominantly exploratory.

For the statistical, hypothesis-testing examinations of HbA1C, fructosamine, CGM readings, and glycemic variability across key time points, we will conduct mixed models (i.e., multilevel model) analyses, which will allow us to quantify within-between interactions, or changes within subjects over time and differences across groups. These models can also include multiple independent variables/covariates.

F. Inclusion/Exclusion Criteria

Inclusion criteria:

1. Pregnancy and Gestation \leq 30 weeks
2. Singleton pregnancy

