RT-CGM and meter will be downloaded for the intervention group and meter downloaded for the control group. Vital signs, weight and medications and dose will be recorded at each visit and results of maternal ultrasound if available (appendix M).

Between Visits: In the weeks between visits participants will continue their routine OB care with their OB providers. The OB providers may or may not be aware that their patient is participating in the study or have knowledge of their study group allocation. The participants will provide their OB providers the usual blood sugar values that they typically supply to their OB provider. For the control group this will be fingerstick glucose values for fasting and 1-hr post-meals. For the intervention group, this will be a log of the CGM

glucose values at the time of fasting and 1-hr post-meals. The OB providers will not be expected to use the CGM system itself.

Delivery: EMR will be reviewed for maternal and fetal outcomes.

I. Randomization/allotment: Randomization/allotment: Once they have signed the consent form, study participants will be randomized to treatment group. The project will use random, permuted blocks within strata to do this. Two participant factors will be considered in creating the strata: 1) weeks pregnant (14-24 weeks or 28 weeks); and 2) pre-pregnancy BMI (≤ 35 and >35). Thus, the strata will be:

Pregnant 14-24 weeks and BMI ≤ 35

Pregnant >24 weeks and BMI ≤ 35

Pregnant 14-24 weeks and BMI >35

Pregnant >24 weeks and BMI >35 .

Separate randomization lists will then be prepared for each of the above strata, using random permuted blocks generated in SAS 9.4. The lists will be transferred (by the statistician) to a sequence of sealed envelopes with the treatment group noted on a card within.

Since this is a small clinical trial, there is the potential problem of uneven distribution of study participants across the strata. However, we believe we have mitigated this potential by having only 4 strata. Also, this approach works better for this project than other approaches (such as the minimization method) due to the relatively greater level of staffing effort required for those approaches to work.

Source: Pocock SJ. 1983. Clinical Trials. A Practical Approach. Chichester, New York: John Wiley & Sons

J. Study Procedures, Materials and Devices :

Televisits:

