Perception/Satisfaction with CGM and Fingersticks/Meter (Appendices J): The Harvard Joslin Diabetes Center has developed a series of questionnaires on CGM experiences, opinions and expectations that will be given at the end of the intervention and has been adapted for the GDM. Additionally, questions about food changes and activity changes that was created for CGM use(19,20) . Questionnaires have been adapted for use in those using only meter fingersticks and for GDM.

Sleep Questionnaire (appendix Q) The Pittsburgh Sleep Questionnaire is good tool for screening sleep disorders in the population and has been used in pregnancy (22,23)

N: Glucose/CGM Data /Evaluation Measures: The compliance and duration wear for participants with CGM will also be recorded. Glucose dynamics, e.g., average glucose, standard deviation, mean amplitude of glucose excursion (MAGE), time in range % (65 and 140 mg/dL), % high (>140 mg/dL), % low (<64 mg/dL), and severe low % (<54mg/dL) and coefficient of variation (CV) and other statistical measures of glucose variability in those with CGM will be reviewed from the RT- CGM device data at baseline and visit 2-4. Blinded CGM values will be obtained at baseline and visit 2 and 3.

Glucose meter: Compliance with fingersticks 4 times a day will be recorded by average number of fingersticks per day. Glucose data including: average glucose, standard deviation, mean amplitude of glucose excursion (MAGE), time in range % (65 and 140 mg/dL), % high (>140 mg/dL), % low (<64mg/dL), and severe low % (<54mg/dL) will also be recorded.

N:Antenatal Ultrasound Markers: estimated fetal weight (in grams and percentile) using Hadlock scale, Biparietal Diameter, Head circumference, abdominal circumference, and femur length. Amniotic Fluid Index.

O: Delivery Outcomes:

Obstetric Outcomes:

- 1.Gestational age at delivery
- 2.Labor status (spontaneous labor, induced labor, no labor). For induced labor include indication for induction
- 3.Mode of delivery (vaginal delivery, cesarean delivery, operative vaginal delivery) including indication for delivery
- 4.Shoulder dystocia: defined as a delivery that requires additional obstetric maneuvers to release the shoulders after gentle downward traction has failed. SD occurs when either the anterior or, less commonly, the posterior fetal shoulder impacts on the maternal symphysis or sacral promontory

Maternal Outcome:

1. Preeclampsia or GHTN
2. Maternal insulin or medication use

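### Aim 5 asks about insulin dose only among women who start insulin, a group formed after randomisation, and no dose analysis in all randomised women is defined

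*Combined protocol and SAP*

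**What the plan says.** Section A, Aim 5, has two consecutive sentences. The first makes initiation an outcome: "Evaluate if RT-CGM decreases need for initiation of oral diabetes medication and/or insulin". The second sets a condition on the dose question: "If insulin initiated, evaluate if RT-CGM reduces cumulative insulin dose".

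The rest of the protocol adds little on dose:

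- **Section E, Data Analysis Plan.** It introduces its mixed models with "For the statistical, hypothesis-testing examinations of HbA1C, fructosamine, CGM readings, and glycemic variability across key time points". Neither insulin dose nor initiation is named. No analysis set is defined, and no value is given for women who never start.
- **Section O, Maternal Outcome.** The only entry is "Maternal insulin or medication use", with no definition of cumulative dose.
- **Section H, visit descriptions.** Medications and their dose are recorded at each visit in both arms. The appendix list includes a follow-up form covering insulin use.
- **Section H, Between Visits.** OB providers "may or may not be aware that their patient is participating in the study or have knowledge of their study group allocation". On what they receive: "For the control group this will be fingerstick glucose values for fasting and 1-hr post-meals" and "For the intervention group, this will be a log of the CGM" readings at the same times.
- **Section I.** Women are randomised in permuted blocks within four strata of gestational age and pre-pregnancy BMI.

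**The concern.** Randomisation makes the arms comparable over everyone randomised. It does not make starters in one arm comparable with starters in the other once the intervention can affect who starts. Aim 5 puts that possibility forward as its own hypothesis.

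Suppose RT-CGM keeps some milder cases off insulin. The RT-CGM starters are then, on average, the women with higher need. Mean dose among starters can rise while total insulin use in the arm falls, so the starters-only result can point the opposite way from the total. If RT-CGM led to more women starting, the distortion would run in its favour.

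Initiation could also differ by arm without any change in glucose, because the log that the provider reads comes from a different device in each arm and the provider may know the allocation.

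Cumulative dose adds a second dependence, on time spent on insulin. That varies with gestational age at entry. Stratification balances entry time over all randomised women, not among starters.

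**Working it through.** **Is there a figure in the plan to reproduce?** No. The only computed figure is the sample size of 92, which is for HbA1c and does not bear on this point.

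**Inputs from the protocol.** 50 women per arm (section D); dose question conditional on starting (section A).

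**Assumed inputs, none in the documents.** Control initiation 30%; RT-CGM initiation 15%, 25%, 30% or 40%; lognormal daily dose need with coefficient of variation 0.5; correlation ρ between log dose need and the severity that triggers starting of 0.5 to 1.0; no effect of RT-CGM on any woman's dose.

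**Formula.** A woman starts when a standard normal severity score exceeds t, so t0 = z(0.70) = 0.524 for control and t1 = z(1 − p1) for RT-CGM. The log-dose SD is σ = √ln(1 + 0.5²) = 0.472. Mean dose per randomised woman, with 0 for non-starters, is proportional to Φ(ρσ − t). Hence:

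- all-randomised ratio = Φ(ρσ − t1) / Φ(ρσ − t0)
- starters-only ratio = all-randomised ratio × 0.30 / p1

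**One case in full (p1 = 15%, ρ = 0.8).** t1 = 1.036 and ρσ = 0.378. Φ(0.378 − 1.036) = 0.255 and Φ(0.378 − 0.524) = 0.442. The all-randomised ratio is 0.255/0.442 = 0.577. The starters-only ratio is 0.577 × 0.30/0.15 = 1.155.

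**Results, RT-CGM/control mean daily dose, at ρ = 0.5 / 0.8 / 1.0:**

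| RT-CGM initiation (control 30%) | Starters only | All randomised |
|---|---|---|
| 15% | 1.096 / 1.155 / 1.195 | 0.548 / 0.577 / 0.598 |
| 25% | 1.026 / 1.041 / 1.051 | 0.855 / 0.868 / 0.876 |
| 30% | 1.000 / 1.000 / 1.000 | 1.000 / 1.000 / 1.000 |
| 40% | 0.957 / 0.933 / 0.918 | 1.276 / 1.244 / 1.224 |

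At ρ = 0 the starters-only ratio is 1.000 whatever the initiation rates. In the 15% row total insulin falls by 40% or more while dose among starters looks 10% to 20% higher.

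**From daily to cumulative dose.** The ratios carry over only if starters in both arms spend the same time on insulin. RT-CGM starters spending 1 − 1/1.155 = 13.4% fewer days on insulin would cancel the 1.155.

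**Against chance.** The 15% v 30% case (ρ = 0.8) was simulated with 50 per arm, which gives about 7.5 and 15 starters. Cumulative dose was taken as daily dose × 14 or 22 weeks × a uniform share of that time on insulin. The starters-only ratio had a 95% range of 0.83-1.60 for daily dose and 0.52-2.22 for cumulative dose. A nominal 5% Welch test on log dose was significant in 14.3% and 7.4% of trials. At 25% v 30% the figures were 6.1% and 4.9%, so little or no inflation.

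**The case against.** The strongest reply is that the protocol specifies no starters-only test. Aim 5 is one line that names no analysis set and no method, and section E is silent on dose altogether. A reader might infer that a biased analysis has been prespecified. The documents do not support that. What stands is narrower: the aim's wording points to starters, and nothing elsewhere defines another comparison.

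A second reply is that the bias is small on the outcome the aim names. For cumulative dose, false significance rises only to 7.4% even when RT-CGM is assumed to halve initiation, and chance scatter is far wider than the bias. Under the aim's own hypothesis the bias runs against RT-CGM: in the same case a starters-only test on cumulative dose falsely favoured it in about 0.6% of trials. This stands, and it limits the severity. It does not make the starters-only contrast interpretable.

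Third, section J says that OB providers will not specifically use the CGM in management decisions. That limits the provider route but does not remove it, because the values they review for the intervention arm are still CGM readings.

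Fourth, time at risk should not be read as fixed at 14 or 22 weeks. Those are visit labels, and the Figure 1 note gives a duration of CGM use without a unit. Entry is allowed from 14 up to 30 weeks, so follow-up varies more continuously.

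Finally, investigators may reasonably want to know dose among users. They can still show it, as description.

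**Conclusion.** The point holds as a gap between the wording of Aim 5 and the analysis plan. Followed as written, the dose question compares two groups selected after randomisation, and no analysis protected by randomisation is offered beside it.

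The selection bias requires both that initiation differ by arm and that starting track dose need. Its size and direction cannot be derived from the documents. The illustrative ratios rest wholly on the assumed 30% control initiation, dose spread and correlation. A reader might take them as evidence that the dose result will be materially wrong, or wrong in favour of RT-CGM; they show neither.

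Severity is minor. Dose is a secondary question in what section B describes with "we are conducting a pilot study of CGM in gestational diabetes". The HbA1c analysis and the sample size do not depend on it, and a comparison of initiation in all randomised women would not share the problem.

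**What to change.** In Aim 5 and section E, state the following:

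- Cumulative insulin dose is compared in all randomised women, as randomised, and counted as 0 if insulin is never started.
- The comparison accounts for the gestational-age and BMI randomisation strata.
- It is reported beside the all-randomised comparison of initiation.
- Dose among starters is descriptive only and is not evidence of an RT-CGM effect.

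The choice of interval or test, and the rule for dose between visits or after withdrawal, can be left to the trial statistician, provided they are written down before analysis. If only one sentence is added, it should be the one labelling starters' dose as descriptive.

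The cost is a short paragraph, since dose is already recorded at each visit. There are three downsides. The outcome has many zeros. It adds little power beyond initiation: in the hypothetical 15% v 30% case with 50 per arm, a stratified bootstrap interval for the cumulative difference excluded 0 in about 27% of trials, against 44% for a chi-square test on initiation. It also answers a slightly different question from dose among users, which remains visible in the descriptive table.

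### The only powered outcome, HbA1c, is in none of the six aims, and the plan tests it with fructosamine and the CGM metrics without naming a primary outcome, deciding contrast or multiplicity rule.

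*Combined protocol and SAP*

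**What the plan says.** Three parts of the document bear on this.

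- **Section A (hypothesis and aims).** The hypothesis is that RT-CGM reduces glycemic variability. Aim 1 is to "Evaluate if Real Time Continuous Glucose Monitoring improves mean glucose, time in range, time above and below range", and it goes on to MAGE, standard deviation and coefficient of variation: seven CGM metrics in all. Aims 2 to 6 cover fetal and maternal outcomes, participant perception, nutrition and lifestyle, medication and insulin need, and nocturnal hypoglycemia. HbA1c is in none of them.
- **Section E, Sample Size Estimation.** "The HbA1C outcome was used for the sample size calculation", with "an alpha of 0.05 and power of 0.80". The effect size f is 0.14. For sphericity and correlation, "We specified both at 0.60". The result is "we need a total of 92 study subjects", and allowing for attrition "we are planning to enroll 100 patients".
- **Section E, Data Analysis Plan.** "For the statistical, hypothesis-testing examinations of HbA1C, fructosamine, CGM readings, and glycemic variability across key time points, we will conduct mixed models". The sentence goes on to say that these models will quantify within-between interactions. Only the review of individual CGM trajectories, with its overlaid values, is described as mainly exploratory.

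Section N adds the percentage of severe low readings and an open-ended set of further variability measures. The text names no primary or secondary outcome, deciding time point or contrast, testing hierarchy, multiplicity adjustment or success criterion. The appendices are listed by title only and are not relied on here.

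**The concern.** The document has two candidates for the result that decides the trial, and they disagree. The power calculation points to HbA1c; the hypothesis and Aim 1 point to CGM metrics. The testing sentence covers both and ranks neither.

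A null HbA1c result with one significant CGM metric could be reported as confirming Aim 1. A significant HbA1c result with null CGM metrics could be reported as success by citing the power calculation. Either report would be consistent with the plan. The 0.05 error rate and 80% power in Section E describe one HbA1c test and do not carry over to a conclusion chosen from several outcomes.

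**Working it through.** **1. The plan's own figure.** Inputs from Section E: f = 0.14, alpha 0.05, power 0.80, sphericity ε = 0.60, correlation ρ = 0.60. Two groups, k = 2 (Section D). HbA1c is measured at baseline, 30-32 and 34-36 weeks (Section K), so m = 3; the sample-size text does not state m.

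For a G*Power within-between interaction:

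- λ = f² × N × m × ε / (1 − ρ)
- df1 = (k − 1)(m − 1)ε and df2 = (N − k)(m − 1)ε

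At N = 92: λ = 0.0196 × 92 × 3 × 0.60 / 0.40 = 8.11, df1 = 1.2, df2 = 108, and power is 0.784. The N for 80% power is 96 at f = 0.14 exactly, and 92 at f = 0.143, which rounds to 0.14. Power is 0.797 at 95 evaluable participants and 0.818 at 100. The stated N is therefore reproduced, allowing for rounding of f, as an arm-by-time test over three HbA1c measurements. A between-group main effect with m = 3 would need 296.

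**2. Number of outcomes.** HbA1c, fructosamine and the seven Aim 1 metrics make nine.

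**3. Chance of at least one false positive.** Assume that each outcome is tested once at two-sided 0.05, that no true effects exist, and that the test statistics share a common correlation r. The documents give no correlations, so a range is shown. Under independence the chance is 1 − 0.95⁹ = 0.370. In favour of RT-CGM only, at 0.025 per test with every metric oriented so that better is positive, it is 1 − 0.975⁹ = 0.204. The other rows are for equicorrelated normal statistics.

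| r | Either direction | Favouring RT-CGM only |
|---|---|---|
| 0 (upper bound) | 37% | 20% |
| 0.5 | 27% | 13% |
| 0.8 | 17% | 8% |
| 0.9 | 12% | 6% |
| Nominal, one test | 5% | 2.5% |

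**4. Sensitivity to the count.** Counting only the four groups named in the testing sentence gives, in either direction, 18.5% (independent), 16% (r = 0.5) and 9% (r = 0.9). Adding severe low % as a tenth outcome gives 40%, 29% and 13%. Every case exceeds 5%.

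**5. Keeping all outcomes co-equal.** With ten outcomes under Bonferroni, alpha is 0.05/10 = 0.005 each. For the same f and m = 3, N is about 162, and power at N = 100 is about 0.51.

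**6. A single-visit HbA1c contrast.** This is not the test in step 1, so its power must be worked out separately. Take equal correlation 0.60 and f = 0.14, with d the peak arm difference in SD units. The standard error of the baseline-adjusted 34-36 week difference at N = 92 is √(4 × (1 − 0.60²)/92) = 0.167.

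- Effect growing linearly (0, ½, 1): d = 2 × 0.14 × √6 = 0.686; ratio to standard error 4.11; power about 98%.
- Effect present by 30-32 weeks and persisting (0, 1, 1): d = 2 × 0.14 × √4.5 = 0.594; ratio 3.56; power about 94%.
- Effect at full size at 30-32 weeks and half that at 34-36 weeks (0, 1, ½): 34-36 week difference 0.343; power about 53%.

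**The case against.** - **HbA1c is in effect singled out.** It carries the only alpha, power and effect size, and it comes first in the testing sentence. It is therefore too strong to say that all outcomes have strictly equal standing. What remains is that its role is never declared and conflicts with the hypothesis and Aim 1.
- **The plan does not state an inflated procedure.** A reader might infer that every outcome is to be tested at 0.05 at each visit. The documents do not support this. The 0.05 is stated only for the sample size, and the testing sentence, read to its end, suggests one longitudinal model per outcome, whose interaction test can cover all time points. The error rates above show what an any-result-counts reading would give; the plan does not commit to that reading.
- **37% is not a realistic figure.** This stands. Time in, above and below range sum to about 100%, and CV is the SD divided by the mean, so independence is not credible. Two-sided figures also count chance results favouring control, which would not be claimed as success for RT-CGM. The one-direction figures are about half as large, but still well above 2.5%.
- **It is a pilot.** Section B uses that word, which weakens the case for elaborate multiplicity control. It does not remove the point, because Section E powers the study at 80% and calls these models hypothesis-testing.
- **Mixed models handle the repetition.** They deal with correlation within one outcome over time, not with error across separate outcomes.

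**Conclusion.** The point holds. The trial is powered on an outcome that its aims omit, and its testing step ranks nothing, so the document does not determine which result decides the trial. This goes beyond a missing label, because the sample size and the aims point to different answers.

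If any one of nine results may count, the false-positive chance is about 12% to 27% for correlations from 0.9 down to 0.5, or about 6% to 13% counting only results in favour of RT-CGM. These figures rest on three assumptions that the documents do not state: one test per outcome, 0.05 for each, and a common correlation.

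Two stronger readings are not supported. The sample size is not wrong on this account: 92 is reproduced once rounding of f is allowed for. Nor do the documents show that HbA1c must be the primary outcome. The stated hypothesis is about glycemic variability, so a CGM metric is an equally legitimate choice, and the choice belongs to the sponsor.

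**What to change.** Before outcomes are compared by arm:

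1. Name one primary outcome and one contrast, tested at two-sided 0.05.
   - HbA1c keeps the existing sample size. The contrast can be the arm-by-time test over baseline, 30-32 and 34-36 weeks, which the calculation matches. It can instead be the baseline-adjusted difference at 34-36 weeks, with its power and assumed effect shape stated.
   - If the sponsor prefers a CGM metric, redo the power statement for that metric.
2. Adjust the model for the randomization strata, and for the baseline value where the contrast allows. Section I must first be reconciled: it describes the later gestational-age category as 28 weeks in one place and as more than 24 weeks in the list of strata.
3. Align Aim 1 with the chosen primary outcome.
4. Make the remaining CGM metrics and fructosamine secondary, either with Holm adjustment or as estimates with confidence intervals and no significance claim.

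The cost is a protocol amendment to the aims as well as to the analysis text, and somewhat less power for each secondary metric if Holm is used. With HbA1c and the arm-by-time test, no extra participants are needed.
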